- Primary progressive, secondary progressive or progressive relapsing MS
- Patients known to have a history of recent drug or alcohol abuse
- Any severe disease other than MS compromising organ function, meaning: history of, or abnormal laboratory results indicative of any significant cardiac, endocrinologic, hematologic, hepatic, immunologic, metabolic, urologic, pulmonary, gastrointestinal, dermatologic, renal and/or other major disease, that in the opinion of the investigators, would preclude the administration of PLP10 for 30 months.
- History of severe allergic or anaphylactic reactions or known specific nutritional hypersensitivity.

Note

During "on intervention treatment" the patients (depending on their pathological status) will be treated according to the normal international guidelines. A thorough record of treatment (or change of treatments) for each patient will be kept. If a patient changes therapy to immunosuppressant or monoclonal antibody or any other treatment on physicians' decision then he/she will be considered as a drop-out; but continue to be medically followed for the intention to treat analyses purposes.

If a clinical documented relapse is reported during "normalization" period the entry baseline EDSS for that patient will be reported as the EDSS score documented at least 4 weeks after the last relapse during this period.

"Normalization period" will be a 6 months period between enrolment and entry baseline (the first 6 months of the trial that patients will be on the intervention treatment for only normalization purposes). For the result analyses this 6 month period will be considered as a period before entry baseline for all four treatment arms.

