A post-hoc analysis will be performed assessing the proportion of patients free from new or enlarging T2 lesions on brain MRI scans at the end of the study for the per-protocol participants of the group receiving the highest effective intervention *vs.* placebo. Comparison will be made only versus the available archival MRI scans up to three months before the enrolment date. MRI scans will be performed and blinded analyzed at an MRI evaluation center.

Additional

Diet nutritional quality control questioner (set-up by the involved clinical dietitian) will also be performed at enrolment and at every scheduled assessment for the evaluation of the patients' diet habits and adherence as well.

Blood Sample

Blood samples will be collected at enrolment, at every scheduled assessment and at every relapse incident; for

- safety and evaluation of the hematological (full blood count) and biochemical analyses at baseline, 12 months and 24months on treatment and compared to enrolment. The same tests will be performed at the end of the extension period
- membrane lipid profile quantitative analysis will be performed (after study completion to
 ensure the blind status of the trial) on the collected and appropriately treated and stored
 red blood cell membrane lipids extracts (a standard protocol will be followed); to confirm
 patients' adherence.

Safety adverse events

Serious adverse events are defined as those that result in admission to hospital, cause prolonged disability or death, or are judged to be life threatening or otherwise medically significant. A safety monitoring committee will be set up.

Drop Outs

The drop outs, at any time and even the drop outs that never received the assigned interventions should be followed like all other participants as required for intention to treat analyses (ITT).

Missing Data Handling

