The key secondary endpoint is the **time to confirmed disability progression** defined as an increase of 1.0 on the EDSS from a baseline score, confirmed after 6 months, with an absence of an ongoing relapse at the time of assessment (progression cannot be confirmed during a relapse) and with no documented relapse during the 6-months period needed for the confirmation. The final EDSS score will also be confirmed 6 months after the end of the study.

Relapses should be treated with methylprednisolone at a dose of 1g intravenously per day, for three consecutive days followed by prednisolone by mouth at a dose of 1mg/kg of weight per day on a tapering scheme for three weeks.

Hematological (full blood count) and Biochemical analyses should be performed at enrolment, baseline, 12 months and 24months and at the end of the extended period; performed at accredited laboratory.

Blood should be collected from all randomized patients at the time of enrolment and at every scheduled clinical assessment and during relapses. Blood tubes should be appropriately labelled including date, patients' code, number of scheduled assessment, for every blood handling step. A portion of 2 ml total blood volume per patient (in anticoagulant solution) should be drawn and stored refrigerated (4°C) for the lipid extraction procedure (from red blood cells) within 24 hrs according to standard protocol.

Sample Size Estimation

Power calculations could not be done before the study because of the lack of information from previous studies on potential effect sizes. Based on the population size of our country and the centre of reference (CING) we believe that we will probably be able to enroll enough patients for this proof-of-concept study. The scientific knowledge/background of the agents used, novelty of the assessed interventions and the study-protocol design/set-up will be contributing to valuable information. Hopefully the "eligible" final enrolled sample size will be enough to collect quality data able to answer the addressed proof-of-concept questioned - efficacy indication. There is no any matter of ethical conflicts since all interventions will be used as adjuvant. Sample size will strictly be based on this subjects' availability parameter.

Brief Statistical Methods

The study will be considered successful if there is a significant difference between the treatments for either of the two endpoints.

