Baseline characteristics will be compared across all intervention groups by ANOVA or Kruskal-Wallis rank test for continuous variables and by an exact chi-squared test for categorical variables, as appropriate.

Each test will be performed with a significance level of 0.05 (P-values will be two-tailed).

Primary Endpoint

Annualized Relapse Rate (ARR):

A Poisson regression/ negative Binomial analysis will be used to analyze this endpoint. The analysis will allow for likely overdispersion due to within-subject correlations by basing standard errors on the empirical estimator of the parameter covariance matrix. The fixed factors in the model will include treatment and relevant pre-specified covariates.

The relapse rate will be calculated as the total number of relapses divided by the total number of patient-years followed for each treatment group. ARR differences will also be calculated among all comparable parameters and reported as percent difference (relative reduction).

Secondary Endpoint

Time to Confirmed Disability Progression:

For the secondary end-point outcome, the time to disability progression, Kaplan–Meier curves will be constructed. A Long-rank and Cox proportional-hazards regression model will be used to analyze this endpoint. The fixed factors in the model will include treatment and relevant prespecified covariates . Additional baseline characteristics will be considered for inclusion in secondary models.

If the usual normality assumptions are not met, the endpoints will then be analyzed by either Poisson regression, using a model similar to the one to be used for the ARR, Wilcoxon Rank-Sum tests, or proportional odds logistic regression models, depending on the nature of the endpoints and whether covariates will be included in the model.

Safety

All treatment emergent signs and symptoms (those that initially occur after taking the first dose of study medication, or those that worsen after taking the first dose of study medication) will be summarized and tabulated according to their severity (mild, moderate, or severe) and relationship (definitely not related, or related) to study medication. The rates will be compared between each group and placebo using Fisher's Exact test.

Missing Data

Missing data of the lost to follow patients will be imputed by use of the last-observation-carried-forward (LOCF) approach.

We thank every and each one of you, for your total cooperation.

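### The one comparison stated for safety bloods is with enrolment, so the laboratory analysis as written does not answer the protocol's question of safety against placebo

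*Protocol*

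**What the plan says.** The Blood Sample section collects full blood count and biochemistry for safety and sets their comparison in one phrase: "biochemical analyses at baseline, 12 months and 24months on treatment and compared to enrolment". It then adds "The same tests will be performed at the end of the extension period", with no comparison attached. Study Procedures and End Points repeats the schedule ("Hematological (full blood count) and Biochemical analyses should be performed at enrolment, baseline, 12 months and 24months", plus the end of the extension) and names no comparison. The same section makes clear that placebo patients are sampled too: "Blood should be collected from all randomized patients at the time of enrolment and at every scheduled clinical assessment".

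The Safety paragraph of Brief Statistical Methods concerns "All treatment emergent signs and symptoms", tabulated by severity and relationship. Its one test is between arms: "The rates will be compared between each group and placebo using Fisher's Exact test". Laboratory values are not mentioned there.

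The Missing Data Handling section states the trial's main questions. The safety question is how safe the interventions are relative to placebo.

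**The concern.** The protocol asks a between-arm safety question. For the bloods, it writes down a within-patient comparison over time. Change from enrolment in an active arm mixes any effect of the formula with whatever else moves laboratory values over 30 months of intervention. The protocol itself supplies some candidates: relapses are treated with steroid courses, and background MS therapy follows guidelines and may change, with changes recorded (Note after the Exclusion Criteria). Ageing and assay drift are further possibilities, though the documents give no size for either.

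The error can run both ways. A drift common to all arms can look like a laboratory harm, and a real effect that opposes the drift can disappear. An asymptomatic change in a liver enzyme or blood count is also the kind of finding that a table of signs and symptoms may miss, so the between-arm test cannot be relied on to catch it.

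**Working it through.** **Step 1. The text.** Setting the sections side by side:

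| Item | Where | Comparison stated |
|---|---|---|
| Safety question | Missing Data Handling | Against placebo |
| Bloods at entry baseline, 12 and 24 months | Blood Sample | With enrolment |
| Bloods at end of extension | Blood Sample | None |
| Laboratory schedule, repeated | Study Procedures and End Points | None |
| Signs and symptoms | Brief Statistical Methods, Safety | Each group against placebo, Fisher |

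The row needed for a placebo-controlled laboratory answer is absent, although the data for it will exist.

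**Step 2. Is enrolment the wrong reference?** No. Entry baseline comes after six months on the assigned intervention, so enrolment is the only scheduled value before treatment. The gap is the missing comparator group; the reference time is sound.

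**Step 3. Illustration of size.** The protocol gives no figure to reproduce: it has no sample size, laboratory SD, correlation, expected shift or named laboratory test. Every input except the 0.05 two-sided level (Brief Statistical Methods) is therefore assumed:

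- n = 10, 20, 30 or 50 patients per arm
- a drift d, the same in all arms, of 0.2, 0.3 or 0.5 SD of the change
- no effect of any formula
- a paired t-test of change from enrolment

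A shift of δ, in SDs of the measurement, corresponds to d = δ / √(2(1 − ρ)), where ρ is the correlation between enrolment and follow-up. At ρ = 0.5 the divisor is √1 = 1, so the two scales coincide.

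The rejection probability is P(|T| > t with n − 1 df at 0.975), where T is noncentral t with noncentrality d√n. For n = 20 and d = 0.3 the noncentrality is 0.3 × √20 = 1.34 and the probability is 0.247.

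| n per arm | d = 0.2 | d = 0.3 | d = 0.5 |
|---|---|---|---|
| 10 | 0.088 | 0.136 | 0.293 |
| 20 | 0.136 | 0.247 | 0.565 |
| 30 | 0.185 | 0.355 | 0.754 |
| 50 | 0.284 | 0.548 | 0.934 |

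These are rates per analyte, arm and time point. A t-test comparing change from enrolment between an active arm and placebo stays at 0.05 under the same assumptions, because the shared drift cancels.

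**Step 4. Masking.** If the drift is +0.3 SD and a formula's true effect is −0.3 SD, the expected change in the active arm is 0.3 − 0.3 = 0. The before-after test then rejects only at its nominal 5%. The contrast with placebo is 0 − 0.3 = −0.3 SD, and the effect is visible in expectation.

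**Step 5. What a placebo comparison would not remove.** Steroid use follows relapses, which happen after randomisation and may differ by arm. Adjusting for the enrolment value does not remove that difference. The between-arm contrast is then the total effect of assignment, including any part that runs through relapses and their treatment.

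**The case against.** The best defence is that the Blood Sample phrase fixes a reference time in a data-collection section. It names no test and does not exclude placebo, and an analysis adjusted for enrolment is compatible with it. The statistical section is headed as brief, a SAP may exist, and models for laboratory values usually belong there. This stands in part: the absence of a laboratory model is no fault in itself. What remains is that the protocol chose to state a comparison for these bloods, and that comparison by itself does not match the stated safety question.

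A reader might go further and infer that the protocol rules out a placebo comparison, or that laboratory harm can no longer be separated from time, MS therapy or steroids. The documents support neither. No sentence excludes placebo, and bloods come from all randomised patients, so between-arm change can be analysed without new data. Nor does the text say whether a laboratory abnormality may be recorded as a sign; if it were, it could enter the Fisher test.

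A reader might also take the exclusion criterion on abnormal laboratory results ("would preclude the administration of PLP10 for 30 months") as defining on-treatment safety markers. It is an entry criterion and does not do that.

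The therapy argument is limited too. Patients enter on at least six continuous months of interferon or glatiramer, or on no treatment; a switch to an immunosuppressant, a monoclonal antibody or any other treatment counts as a drop-out; and the key analysis is per-protocol. Steroid courses and plain passage of time remain.

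Finally, the illustration assumes a drift common to all arms. If steroid use differs by arm, that assumption fails, and so does the exact 5% for the between-arm test.

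**Conclusion.** The point holds as an incomplete comparison. The only comparison stated for haematology and biochemistry is with enrolment, and the stated between-arm safety test does not mention laboratory values. Followed as written, the laboratory analysis does not answer whether the interventions are safe relative to placebo. The shortfall lies in the wording of the analysis, since the randomised data needed to repair it will be collected, and no efficacy endpoint is touched.

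The false-positive rates, about 9% to 93% over the assumed range against 5%, show direction only. They depend on assumed arm sizes, drift, correlation and a paired test, none of which the protocol states.

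**What to change.** In Blood Sample and in the Safety paragraph of Brief Statistical Methods:

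- Keep enrolment as the pre-treatment reference.
- State that each active arm is compared with placebo on the values at entry baseline and at 12 and 24 months on treatment, adjusted for the enrolment value (ANCOVA).
- Report by arm the proportion of patients who move from normal at enrolment to outside the laboratory reference range, compared with placebo by the Fisher test already named.
- Present end-of-extension values descriptively, since they follow 12 months free of intervention.
- Say that these comparisons are exploratory and estimate the total effect of assignment, including any difference in steroid use through relapses.

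The cost is wording only: no extra samples, visits or patients. Between-arm intervals will be wider than before-after ones. There will be many comparisons: 3 active arms × 3 time points = 9 per analyte, or 9 × 0.05 = 0.45 expected false positives per analyte if nothing differs. Estimates with intervals should therefore carry the message, and isolated p-values should not.

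One related item needs reconciling first. Laboratory tests are due at 12 months on treatment, but the scheduled assessments are at 3, 9, 15, 21 and 24 months, with none at 12.

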Due to the nature of the intervention ingredients/agents the protocol of the clinical study is considering a normalization period for the interventions' agents to exert their beneficial effect. The normalization period is used: (a) because the incorporation/normalization of the immune cells' membranes by dietary oral agents is a long time process, (b) because the T-lymphocytes are produced in a very slow rate in adulthood and even much slower in older people, (c) because oral fatty acids need 6 months to have a neurological effect in animal models, (d) to eliminate any placebo effect and regression to the mean, and finally (e) to correct specific body lipid deficiency, and thus accurately record the efficacy as a result of the interventions. It is strongly suggested that specific lipid deficiency need to be "corrected and things be normalized as much as possible" before evaluating their effect.

Primary end points

Primary outcome will be the annual relapse rate (ARR)

- The study is designed to end 30 months after enrolment and neurological and clinical assessments should be scheduled at entry baseline (6 months after enrollment, the end of normalization period) and at 3, 9, 15, 21 and 24 months on-treatment. A 12 month (extension) period (free of intervention) will be followed with relapse recording.
- Patients should be examined within 48 hours after the onset of new neurological symptoms for the treating physician to confirm and record the relapse as per protocol.

Relapses are defined as new neurologic symptoms or worsening of pre-existing symptoms (that are stable for at least 1 month) not associated with fever or infection that lasts for at least 24 hours and characterized by new or worsening neurological signs on examination.

The Key Secondary end point will be the time to confirmed disability progression

Time to confirmed disability progression is defined as an increase of 1.0 on the EDSS from a baseline score, confirmed after 6 months, with an absence of an ongoing relapse at the time of assessment (progression cannot be confirmed during a relapse) and with no documented relapse during the 6-months period needed for the confirmation. Under the same conditions as previously discussed, the final EDSS score should also be confirmed 6 months after the end of the study.

A post-hoc analysis

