This is an ITT study with a proof-of-concept purpose. The main question that has to be answered is primarily the ability of the interventions to reduce the annual relapses rate and secondly the disability accumulation when used in RRMS patients and how safe it is vs. placebo. All patients who prematurely discontinue the study drug will be encouraged to continue in the study and follow-up until the end of the planned treatment period, regardless of the treatments received. The data collected will be included for ITT analyses. The main analysis of ARR will include all confirmed (associated with new or worsening of pre-existing neurological signs, increase of at list 0.5 score on EDSS) relapses during the study, including relapses reported after study drug discontinuation. The lost to follow missing data will be handled by an appropriate statistical

method and included in the intention to treat analysis (ITT). The overall key analysis should be based on per-protocol (excluding all protocol violations) supported by the ITT analyses.

Other:

An independent Data Monitoring Committee (DMC) will monitor and review all clinical trial data on a regular basis (by the funder).

Investigators adherence will be also monitored by DMC through CRF follow up.

Duration of Study per Patient

The clinical study period is approximately 43 months total, including a screening period up to 1 month, a 6 month normalization, 24 months treatment period and 12 months extended follow up period, after completion. The actual research period is for a total of 30 months including 6 months normalization and 24 months treatment periods.

Methods

The whole procedure follows the clinical trial guidelines as required by the USA Food and Drug Administration (FDA), European Medicines Agency (EMA) and according to the standards of the International Conference of Harmonization (ICH). The Clinical study is in agreement with the rules of Good Clinical Practice (GCP).

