Bottling of the interventions will be performed by a group of scientist (always by the same group of scientist) under the supervision of the involved specialist clinical biochemist at every six months. Interventions and placebo will have the same appearance and smell. The intervention will be bottled under the appropriate conditions, in dark bottle under Nitrogen bed; each coded patient will be assigned to a coded intervention or placebo according to the randomization scheme by HIONU. Both Intervention and placebo bottles will be packaged in a blank white carton box containing the dosage calibrated cup. Patients' codes and their representative intervention codes will be safely kept by HIONU. The independent safety/monitoring committee will be the only physical body that will have access on the safety codes; for use only at emergency and when absolutely necessary, when life threatening conditions such as severe site effects are unexpectedly introduced. The interventions will be handled and appropriately stored by the institution pharmacists. A new full bottle of the drug will be handled to a patient when the

previous bottle is empty returned. Pharmacists will keep a detailed record of intervention handling schedule to the patient.

The study is designed to end 30 months after enrolment and clinical assessments should be scheduled at entry baseline and at 3, 9, 15, 21 and 24 months on-treatment. An extra visit is required 6 months after the end of the study to confirm final EDSS score. Patients will be followed for an extended 12 month period with relapse recording. Patients will also be seen by the neurologist at unscheduled visits within 48 hours after the onset of new neurologic symptoms. If a relapse is suspected, the patient should be referred to the neurologist for evaluation and confirmation of any changes in the EDSS score.

Primary outcomes will be the **annual relapse rate** (**ARR**). **Relapses** are defined as new neurologic symptoms or worsening of pre-existing symptoms (that were stable for at least 1 month) not associated with fever or infection that lasts for at least 24 hours characterized by new or worsening neurological sign on examination as defined by previously described EDSS changes. The ARR for each treatment group is the mean of the annualized ARRs for all patients in the group calculated as the total number of confirmed relapses divided by the total number of days on study, multiplied by 365.25.

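### The event counted in the primary annual relapse rate is not worded consistently: the 0.5-point EDSS criterion is missing from the endpoint definition and "confirmed" from the statistical formula

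*Protocol*

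**What the plan says.** Four places in the Protocol bear on which relapses enter the primary ARR.

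- **Primary end points.** A relapse is new symptoms, or worsening of stable ones, without fever or infection, "that lasts for at least 24 hours and characterized by new or worsening neurological signs on examination". No EDSS change is required. The same section has the treating physician confirm and record the relapse.
- **Missing Data Handling.** The main ARR analysis is to include all "confirmed (associated with new or worsening of pre-existing neurological signs, increase of at list 0.5 score on EDSS) relapses during the study". This is the only place where an EDSS figure is attached to a relapse.
- **Study Procedures and End Points.** The definition is repeated, but the sign is now "new or worsening neurological sign on examination as defined by previously described EDSS changes". No figure is given. The ARR formula that follows has confirmed relapses in its numerator. For a suspected relapse, "the patient should be referred to the neurologist for evaluation and confirmation of any changes in the EDSS score".
- **Brief Statistical Methods, Primary Endpoint.** "The relapse rate will be calculated as the total number of relapses divided by the total number of patient-years followed for each treatment group". The word confirmed does not appear.

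**The concern.** A relapse with a new sign on examination but an unchanged EDSS score is an event under the definition in Primary end points, and is not excluded by the formula in Brief Statistical Methods. It is not an event under Missing Data Handling or, on its natural reading, under Study Procedures and End Points. The same term therefore carries two meanings within the primary endpoint.

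The word confirmed does not settle this by itself. Next to the definition in Primary end points, it can mean that the physician verified the relapse. Under Missing Data Handling, it means that the EDSS rose by at least 0.5.

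The Protocol calls the study successful if either of its two endpoints shows a significant difference, so the ARR count alone can decide the result. If the event is not fixed in advance, two ARRs and two P-values are available for the same patients, and each can be traced to a sentence in the Protocol.

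**Working it through.** The Protocol gives no relapse rate, sample size or power for this point, so there is no figure to reproduce. The check is a comparison of texts, followed by an illustration on assumed inputs.

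**Step 1: the wording side by side**

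| Section | EDSS criterion | Numerator | Is a relapse with a new sign and unchanged EDSS counted? |
|---|---|---|---|
| Primary end points | none | not stated | yes |
| Missing Data Handling | rise of at least 0.5 | confirmed relapses | no |
| Study Procedures and End Points | refers back, no figure | confirmed relapses | no, if the reference is to 0.5 |
| Brief Statistical Methods | none | relapses | yes, as worded |

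**Step 2: which figure the cross-reference means.** Two EDSS changes have been described by that point: 0.5 for relapses, and 1.0 for confirmed disability progression. The 1.0 change must be confirmed after 6 months, with no ongoing relapse and no documented relapse in that period. It cannot be the criterion for a relapse, so 0.5 is the only candidate.

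**Step 3: what the threshold does to the estimate.** Let f0 and f1 be the shares of sign-based relapses that meet the threshold on placebo and active treatment. The Protocol gives neither.

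- Confirmed ARR in an arm = f × sign-based ARR.
- Confirmed rate ratio = sign-based rate ratio × f1/f0.

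If f0 = f1, the expected rate ratio does not change; the ARR is multiplied by 0.95, 0.90 or 0.80 for shares of 95%, 90% or 80%. With f1 = 0.80 and f0 = 0.90, the rate ratio is multiplied by 0.80/0.90 = 0.89.

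**Step 4: an illustration of precision.** All inputs are assumptions: sign-based placebo rate 0.8 per year, sign-based rate ratio 0.60 (active rate 0.48), 2 years of follow-up, negative binomial dispersion k = 0.5, 40 patients per arm, two-sided 0.05. Only the significance level and the 24-month on-treatment period come from the Protocol.

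Var(log RR) = 1/(n·T·r0) + 1/(n·T·r1) + 2k/n, with r0 = 0.8·f0 and r1 = 0.48·f1.

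Power = Φ(|log RR|/SE − 1.96) + Φ(−|log RR|/SE − 1.96).

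For f0 = f1 = 1: Var = 1/64 + 1/38.4 + 1/40 = 0.0667, SE = 0.258, |log 0.60|/SE = 0.511/0.258 = 1.98, power 51%.

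For f0 = f1 = 0.8: Var = 1/51.2 + 1/30.72 + 1/40 = 0.0771, SE = 0.278, power 45%.

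| f0 (placebo) | f1 (active) | Placebo ARR | Rate ratio | Power, 40 per arm |
|---|---|---|---|---|
| 1 | 1 | 0.80 | 0.60 | 51% |
| 0.8 | 0.8 | 0.64 | 0.60 | 45% |
| 0.6 | 0.6 | 0.48 | 0.60 | 38% |
| 0.90 | 0.80 | 0.72 | 0.53 | 63% |
| 0.80 | 0.65 | 0.64 | 0.49 | 70% |
| 0.65 | 0.80 | 0.52 | 0.74 | 19% |

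With 20 per arm, the first three rows give 29%, 26% and 22%. The last three rows need relapse severity to differ between arms, and nothing in the Protocol indicates that it does.

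**The case against.** The strongest reply is that the primary event is already fixed. Missing Data Handling says in terms what the main ARR analysis includes. Study Procedures and End Points, where the ARR is defined, ties the sign to EDSS changes and counts confirmed relapses. On this view Primary end points gives a clinical definition, Missing Data Handling says which of those relapses are analysed, and the formula in Brief Statistical Methods uses a term already defined. Much of this stands: the two sections that specify the counted event agree, and the other two are better read as incomplete than as rival endpoints.

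The reply does not remove the point. The Protocol never describes two tiers of relapse. The reader has to find the threshold under a heading about missing data, resolve a cross-reference that gives no number, and set aside the wording of both the endpoint section and the statistical section.

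Two practical objections also carry weight. There is one centre, with one designated neurologist scoring the EDSS, and suspected relapses are referred for confirmation of EDSS changes, so either count should be recoverable. Statisticians are to be unaware of assignments during the study. Together these limit the harm to a choice made at analysis, and they are the reason for making that choice before unblinding.

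A reader might infer from the cross-reference that a 1.0-point rise could also define a relapse. The documents do not support that: 1.0 belongs only to progression, which cannot be confirmed during a relapse.

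**Conclusion.** The inconsistency is real and affects the primary endpoint. The most natural primary event is the confirmed relapse with an EDSS rise of at least 0.5, but two of the four places as worded would also count relapses without any EDSS change. That leaves a choice open which should be closed before the counts are seen by arm.

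The size cannot be derived from the Protocol. It depends on the share of relapses that meet the threshold and on whether that share differs by arm. With equal shares only the ARR level and the precision move. The power figures above show the direction and rough scale under assumed inputs and are not estimates for this trial.

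A reader might conclude that the Protocol supports several primary counts equally, or that the treatment effect is biased. Neither follows. The text favours one count, and a shift in the rate ratio requires an unequal share that the documents do not suggest. Whether the ARR is averaged over patients or pooled over patient-years is a separate matter.

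**What to change.** Reconcile the four places before unblinding, using the Protocol's own definition from Missing Data Handling:

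1. In Primary end points, state that the event for the primary ARR is a confirmed relapse: the existing criteria plus an EDSS increase of at least 0.5.
2. In Study Procedures and End Points, replace the reference to earlier EDSS changes with the figure, an increase of at least 0.5.
3. In Brief Statistical Methods, make the numerator *total number of confirmed relapses*.
4. Report the ARR of all relapses that meet the present wording of Primary end points, without the EDSS criterion, as a labelled sensitivity analysis and not as the primary result.

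The Protocol does not say which EDSS score the 0.5 rise is measured from. The sponsor should specify it in the same edit.

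The cost is wording in three sections and one extra analysis. No new assessment is needed, since suspected relapses are already referred for confirmation of EDSS changes. The downside is that relapses without an EDSS change leave the primary count, so the ARR is lower and its precision somewhat reduced. In the illustration, the standard error of the log rate ratio rises from 0.258 to 0.278 if 80% of relapses meet the threshold in both arms.
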